6.4. Study Intervention Compliance

When study intervention is administered as an IV infusion or SC injection by qualified staff, the details of each administration will be recorded in the eCRF. For IV infusions, this will include date and start and stop times of the IV infusion and volume infused; for SC injections, this will include date and time of SC injection.

Participants will receive instructions on compliance with study intervention when they begin self-administration of study intervention at home. When participants begin self-administration at home, the investigator or designated study personnel will maintain a log of all study intervention dispensed and returned.

When study intervention is self-administered by participants at home, participants will record all study interventions on a diary card.

Additional details may be provided in the site IPPM and IPPI that is provided separately. Compliance with the treatment schedule is strongly encouraged.

6.5. Concomitant Therapy

Prestudy therapies administered up to 30 days before the first dose of study intervention must be recorded on the eCRF. Any COVID-19 vaccines administered, regardless of timing, must be recorded on the eCRF. Concomitant therapies must be recorded throughout the study, from signing of the informed consent to the last study visit.

All therapies (prescription or over-the-counter medications, including vaccines, vitamins, herbal supplements; non-pharmacologic therapies such as electrical stimulation and acupuncture) different from the study intervention must be recorded in the eCRF.

Recorded information will include a description of the type of therapy, treatment period, dosage, route of administration, and indication. Modification of an effective pre-existing therapy should not be made for the explicit purpose of entering a participant into the study.

Participants who are receiving oral 5-ASA compounds, oral corticosteroids, 6-MP, AZA, or MTX for the treatment of UC at baseline (ie, Week I-0) should maintain a stable dose for the specified period before baseline, as defined in the Inclusion Criteria (Section 5.1).

In general, participants who are receiving these medications for UC at baseline of either Induction Study 1 or Induction Study 2 (ie, Week I-0) should maintain a stable dose through Week M-44, except for oral corticosteroids. Therapies can only be discontinued or reduced in dose after Week I-0 if investigator judgment requires it because of toxicity or other medical necessity; even if the toxicity resolves, the therapy should not be restarted. Oral corticosteroids must be maintained at baseline doses during Induction Study 1 and Induction Study 2, and all participants must begin tapering oral corticosteroids at Week M-0 of the Maintenance Study, unless medically not feasible (for additional details, see Section 6.5.1).

Enrolled participants should not **initiate** any of the following concomitant UC-specific medical therapies at any time during any of the 3 studies:

- Oral or rectal 5-ASA compounds.
- Oral, parenteral, or rectal corticosteroids, including budesonide and beclomethasone dipropionate.
- 6-MP, AZA, or MTX.
- Antibiotics as a primary treatment for UC.
- Total parenteral nutrition or enteral nutrition as a treatment for UC.

If the above medical therapies are initiated or medication doses are changed based on medical necessity as assessed by the investigator, participants should continue to attend all study visits and have all assessments. While this does not represent a deviation from the study protocol, and the participants may remain on their assigned study intervention, participants who initiate or increase the dose above baseline of these UC medications during induction (ie, Induction Study 1 or Induction Study 2) will not be eligible to enter the Maintenance Study. Treatment failures due to UC medication changes will be defined in the SAP.

Laxatives should generally be avoided and should be used only in preparation for endoscopy or other procedures.

The sponsor must be notified in advance (or as soon as possible thereafter) of any changes in concomitant therapy as noted above.

6.5.1. Corticosteroids

As mentioned in Section 6.5, oral corticosteroids for UC **should not be initiated or have the dose increased above baseline** during all 3 studies. The one exception is that participants may

transiently (ie, for ≤ 4 weeks) use increased doses of corticosteroids **for reasons other than** worsening of UC (eg, stress doses of corticosteroids for surgery, asthma flare, adrenocortical insufficiency) during the Maintenance Study.

For participants who are receiving oral corticosteroids on entry into the Maintenance Study, the investigator must begin tapering the daily dose of corticosteroids beginning at Week M-0 (Table 5). Tapering of the daily dose of corticosteroids may be paused for participants meeting clinical flare criteria as described in Section 4.1.3.1. For participants whose corticosteroid taper is interrupted, investigators are encouraged to resume tapering within 4 weeks if clinically appropriate. Tapering may exceed this schedule only if warranted by medical necessity (eg, participant experiencing corticosteroid-related side effects).

Table 5: Recommended Tapering Schedule for Oral Corticosteroids	
Recommended Tapering Schedule for Oral Corticosteroids (Other than Oral Budesonide and Oral Beclomethasone dipropionate)	
Dose >15 mg/day prednisone or equivalent:	Taper daily dose by 5 mg/week until receiving 10 mg/day, then continue tapering by 2.5 mg/week until 0 mg/day
Dose 11 to 15 mg/day prednisone or equivalent:	Taper daily dose to 10 mg/day for 1 week, then continue by 2.5 mg/week until 0 mg/day
Dose ≤ 10 mg/day prednisone or equivalent:	Taper daily dose by 2.5 mg/week until 0 mg/day
Recommended Tapering Schedule for Oral Budesonide and Oral Beclomethasone dipropionate	
Participants receiving oral budesonide or oral beclomethasone dipropionate should have their daily dose tapered according to local clinical practice until 0 mg/day.	

6.5.2. Prohibited Medications/Therapies

Participants who initiate the following treatments will be discontinued from further study intervention administration and should have a final safety follow-up visit approximately 12 weeks after their last dose of study intervention:

- Immunomodulatory agents other than 6-MP, AZA, or MTX (including, but not limited to, 6-thioguanine, cyclosporine, mycophenolate mofetil, tacrolimus, sirolimus, tofacitinib, and other JAK inhibitors).
- Immunomodulatory biologic agents (including, but not limited to, TNF α antagonists, ustekinumab, vedolizumab, abatacept, anakinra).
- Experimental IBD medications (including, but not limited to, upadacitinib, filgotinib, ozanimod, etrolizumab, brazikumab, mirikizumab, risankizumab) or other investigational medications/therapies.
- Thalidomide or related agents.

The sponsor must be notified in advance (or as soon as possible thereafter) of any instances in which prohibited therapies are administered.

6.5.3. Vaccinations (Including COVID-19)

When considering use of locally-approved (including emergency use-authorized) COVID-19 vaccines in study participants, consider protocol lifestyle considerations (Section 5.3) and follow

applicable local vaccine labeling, guidelines, and standards of care for patients receiving immune-targeted therapy.

For study participants receiving a locally-approved (including emergency use-authorized) COVID-19 vaccine, in order to help identify acute reactions potentially related to the COVID-19 vaccine, it is recommended that, where possible, vaccine and study intervention be administered on different days, separated by as large an interval as is practical within the protocol.

6.6. Dose Modification

Any dose/dosage adjustment should be overseen by medically-qualified study-site personnel (principal or subinvestigator unless an immediate safety risk appears to be present).

Details regarding the management of clinical flare and loss of clinical response in participants during the Maintenance Study are provided in Section 4.1.3.1.

[figure not shown]
6.6.1. Phase 3 Maintenance Study

Participants who were rerandomized in the Maintenance Study (ie, guselkumab clinical responders at Week I-12 and placebo crossover responders at Week I-24) and meet criteria for loss of clinical response (ie, no longer satisfies the definition of clinical response as previously defined in Section 3) will be eligible to receive a single blinded dose adjustment as described below and in Figure 6:

- Guselkumab 200 mg SC q4w group: Participants will continue on guselkumab 200 mg SC q4w (ie, no adjustment).
- Guselkumab 100 mg SC q8w group: Participants will adjust to receive guselkumab 200 mg SC q4w.
- Placebo SC: Participants will adjust to receive guselkumab 200 mg SC q4w.

Guselkumab 24-Week responders will continue to receive guselkumab 200 mg SC q4w. Participants induced into clinical response at Week I-12 with placebo will continue to receive SC placebo and are not eligible for a dose adjustment.

Figure 6: Dose Adjustment Treatment Groups in the Maintenance Study for Participants in Clinical Response Following Induction

(R) = Randomization

* Dose adjustment for loss of response may occur beginning at Week M-8, but no later than Week M-32.

† A decrease from induction baseline of ≥ 2 in the partial Mayo score

2772_v2

Participants are only eligible for a single blinded dose adjustment (ie, the first time loss of response criteria are met). The first visit at which a participant can be considered for a dose adjustment is Week M-8. In order to allow sufficient time to assess benefit after dose adjustment, the Week M-32 visit will be the final visit when loss of clinical response criteria (and subsequent dose adjustment) can occur.

Participants who have dose adjusted will be assessed 12 weeks after the visit where the loss of clinical response criteria was met to determine if benefit was achieved from the dose adjustment. Participants who have not shown improvement in their UC activity at that time (as assessed by the partial Mayo response) will be discontinued from study intervention and should return for a final safety visit approximately 12 weeks after their last dose of study intervention. Participants assessed by the investigator to be clinically improved (partial Mayo response) will continue to receive the same adjusted dose in a blinded manner.

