4.1.3.1. Management of Clinical Flare and Loss of Clinical Response

During the Maintenance Study, participants who meet the following criteria will be considered to be in clinical flare:

- an increase from maintenance baseline in the partial Mayo score (ie, the Mayo score without the endoscopy subscore) of at least 2 points and an absolute partial Mayo score ≥ 4 ;
- OR
- an absolute partial Mayo score ≥ 7 points (Section 8.1.1).

Participants in clinical flare between Week M-4 and Week M-32 (inclusive) will be evaluated for loss of clinical response based on the modified Mayo score that includes the endoscopy subscore assigned by the local endoscopist relative to their induction baseline Mayo score. Loss of clinical response means that a participant no longer satisfies the following definition of clinical response:

- a decrease from induction baseline in the modified Mayo score by $\geq 30\%$ and ≥ 2 points, with either a ≥ 1 -point decrease from baseline in the rectal bleeding subscore or a rectal bleeding subscore of 0 or 1.

The management of clinical flare and loss of clinical response during the Maintenance Study is summarized in [Figure 5](#) and described below.

Participants in clinical flare for the first time between Week M-4 and Week M-32 (inclusive) should undergo endoscopy, which need only be a sigmoidoscopy, and be evaluated for loss of clinical response ([Table 2](#) footnote b). These participants should maintain stable doses of their UC medications after meeting clinical flare criteria and while waiting for their endoscopy subscore to establish loss of clinical response. Participants who meet the criteria for loss of clinical response will be eligible for a single blinded dose adjustment as detailed in Section 6.6.1. The dose adjustment can only start between Weeks M-8 and M-32.

[figure not shown]
Participants are strongly encouraged to undergo endoscopy at the time of first clinical flare to establish if loss of clinical response criteria were met. A participant who declines to undergo an endoscopy on initial clinical flare of UC will be discontinued from study intervention administration and should return for a final safety visit approximately 12 weeks after their last dose of study intervention.

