Participants who meet the criteria for loss of clinical response will be assessed 12 weeks after the visit at which the loss of clinical response criteria were met. During this 12-week interval, clinical flare criteria will not be applied. Participants who have not achieved a partial Mayo response (ie, a decrease from induction baseline of ≥ 2 in the partial Mayo score) at 12 weeks after meeting the criteria for loss of clinical response will be discontinued from study intervention administration and should return for a final safety visit approximately 12 weeks after their last dose of study intervention.

Participants who are assessed as being in partial Mayo response 12 weeks after loss of clinical response will continue in the study and continue to be assessed for clinical flare using the criteria based on the partial Mayo score.

A participant who meets the criteria of clinical flare on more than 1 occasion will not undergo a second evaluation for the loss of clinical response and may be discontinued from study intervention administration. If discontinued, the participant should return for a final safety visit approximately 12 weeks after their last dose of study intervention. Refer to considerations for discontinuation of study intervention for worsening of UC (Section 7.1.2).

Figure 5: Management of Clinical Flare and Loss of Clinical Response During the Maintenance Study

* A decrease from induction baseline of ≥ 2 in the partial Mayo score.

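### The 12-week check of benefit from dose adjustment is counted from the loss-of-response visit, so a loss established at Week M-4 could be judged 8 weeks after adjustment instead of 12

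*Protocol*

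**What the plan says.** Protocol 6.6.1 fixes the timing of the check: "Participants who have dose adjusted will be assessed 12 weeks after the visit where the loss of clinical response criteria was met". It gives the purpose as "to determine if benefit was achieved from the dose adjustment". It closes the window for loss and adjustment at M-32 for a stated reason: "In order to allow sufficient time to assess benefit after dose adjustment, the Week M-32 visit will be the final visit" at which they can occur.

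Protocol 4.1.3.1 sets two different opening visits. For loss: "Participants in clinical flare between Week M-4 and Week M-32 (inclusive) will be evaluated for loss of clinical response". For the adjustment: "The dose adjustment can only start between Weeks M-8 and M-32". Between the two, participants keep their UC medication stable "while waiting for their endoscopy subscore to establish loss of clinical response".

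The check is binding. Under 4.1.3.1, participants without a partial Mayo response "at 12 weeks after meeting the criteria for loss of clinical response will be discontinued from study intervention administration". Until then, "During this 12-week interval, clinical flare criteria will not be applied".

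The SAP words the sequence differently. Section 1.3 describes eligibility as loss at a scheduled visit from M-8 to M-32. Section 1.3.1 speaks of confirmed loss in that window and times the check from a visit at which the loss criteria are met and the adjustment takes place. Section 5.7 follows adjusted participants through 12 weeks after adjustment.

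**The concern.** The check is meant to show whether the adjusted dose helped, but its clock starts at the loss of response. The two starting points coincide when loss and adjustment fall on the same visit. They cannot coincide for a loss established at M-4, because the adjustment has to wait until M-8. The same mandatory stopping rule would then act after a shorter trial of the adjusted dose.

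What is at stake is who is taken off treatment. A participant moved from placebo to 200 mg q4w could be stopped before the third adjusted dose. Such a stop also carries into the two SAP analyses that look past the adjustment (5.7 and 5.8).

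**Working it through.** **Inputs.** Loss evaluated from M-4 to M-32 and adjustment from M-8 to M-32 (protocol 4.1.3.1, 6.6.1). Check 12 weeks after the loss visit (4.1.3.1, 6.6.1). Dosing every 4 weeks, with assessments done before dosing (Table 2, footnote g). Visits are taken at their nominal weeks; the ±10-day windows are ignored.

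**Formulas.** Check = loss visit + 12. Earliest adjustment = the later of M-8 and the loss visit. Time on adjusted dose = check − adjustment.

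**The plan's own figure first.** A loss at M-32 adjusted at the same visit is checked at 32 + 12 = M-44. That is 12 weeks on the adjusted dose, which agrees with the stated reason for the M-32 cutoff.

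**All scheduled visits:**

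| Loss established | Earliest adjustment | Check | Weeks on adjusted dose | Adjusted doses before check |
|---|---|---|---|---|
| M-4 | M-8 | M-16 | 16 − 8 = 8 | 2 (M-8, M-12) |
| M-8 | M-8 | M-20 | 20 − 8 = 12 | 3 (M-8, M-12, M-16) |
| M-12 to M-28 | same visit | loss + 12 | 12 | 3 |
| M-32 | M-32 | M-44 | 44 − 32 = 12 | 3 (M-32, M-36, M-40) |

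Among scheduled visits with the earliest possible adjustment, only M-4 falls short: 8/12 = 67% of the 12 weeks. A loss at an unscheduled visit, or an adjustment delayed while the endoscopy subscore is awaited, could shorten the interval in the same way.

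**Drug received from the loss visit to the check, loss at M-4:**

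- Placebo arm: 2 × 200 = 400 mg, against 3 × 200 = 600 mg when loss and adjustment share a visit.
- 100 mg q8w arm: 100 mg at M-4 (6.1.3 starts this regimen there) + 400 = 500 mg in three doses, against 600 mg. The shortfall is smaller.
- 200 mg q4w arm: the adjustment is a sham and the dose does not change, so no exposure is lost.

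**Effect on the analyses.**

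- Primary and major secondary endpoints: a real or sham dose adjustment is intercurrent event 2 and already counts as failure (SAP 5.3.2, 5.4.1.2). Nothing changes.
- SAP 5.8: event 2 is suspended but discontinuation (event 4 or 6) is not. A stop at M-16 therefore makes the M-44 outcome a failure.
- SAP 5.7: twelve weeks after an M-8 adjustment is M-20. A participant stopped at M-16 has no scheduled M-20 value. Symptomatic remission is imputed as non-response, and continuous measures stay missing.

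**The case against.** The strongest answer is that the documents allow a reading with no shortfall. Flare is judged on the partial Mayo score, but loss of response needs an endoscopy subscore, and 4.1.3.1 provides for waiting for it. On that reading M-4 opens the flare window, and M-8, one dosing visit later, is when loss is confirmed and acted on. Several details fit. Table 2 attaches footnote b to the M-8 to M-32 columns but not to M-4, and SAP 1.3 and 1.3.1 place loss from M-8. Figure 5, which summarises the algorithm, is not in the text available here and may settle the matter. This objection stands to the extent that the shortfall is possible rather than certain. It does not remove the point: 4.1.3.1 names M-4 for the evaluation of loss, the text of footnote b covers any first flare before M-32, and no available protocol text delays confirmation to M-8.

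A second answer is that counting from loss protects participants, since flare criteria are suspended until the check and a later check leaves active disease longer. That is a real trade-off. It is limited, because 7.1.2 keeps discontinuation for worsening UC available, and it sits poorly with the purpose that 6.6.1 gives for the check.

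A third is that those stopped have not reached even a 2-point fall in partial Mayo score from induction baseline, so many would fail at M-20 as well. This is plausible and keeps the consequence small, but the documents give no data on it.

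Two stronger readings are tempting. A reader might infer that the trial's main results are affected; SAP 5.3.2 rules that out, because adjusted participants are failures whatever happens later. A reader might also infer that the SAP contradicts the protocol and must be rewritten. Its wording already ties the check to the adjustment visit and gives the full 12 weeks, so the text to correct is the protocol's.

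**Conclusion.** The point holds as a minor one. As written, the protocol permits a mandatory stop at M-16 for a participant whose loss is established at M-4, after 8 weeks and two adjusted doses instead of 12 weeks and three. This assumes that loss can be established at M-4 itself and that adjustment follows at the first permitted visit; if loss is confirmed only at M-8, the shortfall is zero.

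That 12 weeks after adjustment is the intended time is an inference. It rests on the stated purpose of the check and on SAP 1.3.1 and 5.7. The M-32 cutoff fits it but would equally fit 12 weeks after loss.

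The number affected is not given and is probably small. For scale only, each 1% of the 161 planned per arm is 161 × 0.01 = about 1.6 participants. The shortened trial bears mainly on placebo, less on 100 mg q8w and not on 200 mg q4w, so any extra failures in SAP 5.8 would fall mainly in the placebo arm. SAP 5.7 is descriptive, and 5.8 lies outside the multiplicity-controlled testing.

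**What to change.** In protocol 4.1.3.1 and 6.6.1, count the 12 weeks, and the suspension of flare criteria that goes with them, from the real or sham dose-adjustment visit. This matches SAP 1.3.1 and 5.7, so no SAP change is needed. The wording should also say that the flare that led to the adjustment is not counted again while the participant waits for it, since 4.1.3.1 allows discontinuation for a repeat flare.

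An M-4 loss adjusted at M-8 is then checked at 8 + 12 = M-20, after three adjusted doses (M-8, M-12, M-16). Checks for same-visit cases do not move, and the latest stays at M-44.

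The cost is wording in two protocol sections. The downside is that for a few participants the stop decision comes up to 4 weeks later (20 − 4 = 16 weeks after loss instead of 12), with discontinuation under 7.1.2 still available throughout. If the sponsor means loss to be established only from M-8, stating that in 4.1.3.1 would also close the M-4 gap.

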6.7. Intervention After the End of the Study

Participants will be instructed that study intervention will not be made available to them after they have completed/discontinued study intervention and that they should return to their primary physician to determine standard of care. Local regulations on continued access will take precedence.

7. DISCONTINUATION OF STUDY INTERVENTION AND PARTICIPANT DISCONTINUATION/WITHDRAWAL

If a participant discontinues study intervention or withdraws from the study before the end of the study, assessments should be obtained as specified in the SoA (Section 1.3).

7.1. Discontinuation of Study Intervention

A participant who discontinues study intervention will not be automatically withdrawn from the study (see Section 7.2).

7.1.1. Conditions That Require Study Intervention Discontinuation

A participant's study intervention must be discontinued under the following conditions:

1. The participant (or the participant's representative) withdraws consent to receive study intervention.
2. The investigator believes that for safety or tolerability reasons (eg, adverse event), it is in the best interest of the participant to discontinue study intervention.
3. The participant becomes pregnant or plans a pregnancy within the study period. Refer to Appendix 6 (Section 10.6), Contraceptive and Barrier Guidance and Collection of Pregnancy Information.
4. The participant initiates treatment with prohibited therapies for UC (Section 6.5.2).
5. The participant has a colectomy.
6. The participant develops an opportunistic infection.
7. The participant is deemed ineligible according to the following TB screening criteria:

A diagnosis of active TB is made.

A participant has symptoms suggestive of active TB based on follow-up assessment questions and/or physical examination or has had recent close contact with a person with active TB and cannot or will not continue to undergo additional evaluation.

A participant undergoing evaluation has a chest radiograph with evidence of current active TB and/or a positive QuantiFERON-TB[®] (or T-SPOT[®] for sites in Japan) test result (and/or a positive tuberculin skin test result in countries/territories in which the QuantiFERON-TB[®] test is not approved/registered or the tuberculin skin test is mandated by local health authorities), unless active TB can be ruled out and appropriate treatment for latent TB can be initiated prior to the next study intervention administration and continued to completion (see also Section 8.2.11 and Appendix 5 [Section 10.5]). Indeterminate QuantiFERON-TB[®] (or borderline T-SPOT[®] for sites in Japan) test results should be handled as described in Section 8.2.11. Participants with persistently indeterminate QuantiFERON-TB[®] (or borderline T-SPOT[®] for sites in Japan) test results may continue without treatment for latent TB if active TB is ruled out, their chest radiograph shows no abnormality suggestive of TB (active or old, inactive TB) and the participant has no additional risk factors for TB as determined by the investigator. This determination must be promptly reported to the medical monitor or designee and recorded in the participant's source documents and initialed by the investigator.

Note: In Ukraine, while the QuantiFERON-TB® test is not approved/registered, it is acceptable, and an additional tuberculin skin test is not required.

A participant receiving treatment for latent TB discontinues this treatment prematurely or is noncompliant with the therapy.

8. The participant has a serious adverse reaction that is related to an injection or an infusion resulting in bronchospasm with wheezing and/or dyspnea that requires ventilatory support **OR** that results in symptomatic hypotension with a decrease in systolic blood pressure >40 mm Hg or blood pressure <90/60 mm Hg.
9. The participant has a reaction resulting in myalgia and/or arthralgia with fever and/or rash (suggestive of serum sickness and not representative of signs and symptoms of other recognized clinical syndromes) occurring 1 to 14 days after an injection of study intervention. These may be accompanied by other events including pruritus, facial/hand/lip edema, dysphagia, urticaria, sore throat, and/or headache.
10. The participant has a malignancy including squamous cell skin cancer. Consideration may be given to allowing participants who develop ≤ 2 basal cell skin cancers that are adequately treated with no evidence of residual disease to continue to receive study intervention.
11. The participant has severe liver test abnormalities that are not transient and are not explained by other etiologies, as described in Section 8.2.4 and Appendix 9 (Section 10.9; Guideline Algorithm for Monitoring, Assessment, and Evaluation of Abnormal Liver Tests in Participants With No Underlying Liver Disease). Such abnormalities would include the following:
 - ALT or AST >8 x the upper limit of normal (ULN)
 - ALT or AST >5 x ULN for more than 2 weeks
 - ALT or AST >3 x ULN **and** total bilirubin >2 x ULN **or** international normalized ratio (INR) >1.5
 - ALT or AST >3 x ULN and symptoms of hepatitis (eg, fatigue, nausea, vomiting, right upper quadrant pain or tenderness, fever, rash, and/or eosinophilia [>5%])

